## **4.2 Analysis methods**

### **4.2.1 Analysis of the primary variable**

For the primary variable, time from randomisation to first subsequent stroke or death, the null hypothesis of no treatment effect,  $H_0$ : HR (ticagrelor divided by placebo) = 1, versus the alternative hypothesis,  $H_1$ : HR  $\neq$  1, will be tested at the 4.996% 2-sided significance level.

In the summary table of the primary analysis, separate analyses of each of the components (stroke, death) will also be presented.

If there are patients lost to follow-up in the ticagrelor group, a sensitivity (“tipping point”) analysis may be performed by adding events to the ticagrelor group (at the time of censoring) until a non-significant result is obtained.

A sensitivity analysis ‘on treatment’ will be performed, including events from the date of the first dose of IP up to the date of the last dose of IP + 7 days (inclusive). Event-free patients will be censored at the date of the last dose of IP + 7 days or the date of last event assessment, whichever occurs earlier. Patients who never received any dose of IP will be censored at Day 1.

As an explorative analysis, primary events up to the end of the follow-up period will be analysed by repeating the primary analysis with event-free patients censored at Visit 4 (or Day 64) instead of Visit 3 (or Day 34). If Visit 4 has occurred within the visit window, Day 60 to 64, events will be included up to the date of Visit 4 (inclusive). If Visit 4 has occurred outside of the visit window (or is missing), it will be replaced by Day 64 for event inclusion and censoring.

#### **4.2.1.1 Subgroup analyses of the primary variable**

Subgroup analyses of the primary variable will be performed to evaluate variation of treatment effect. Tests for interaction between treatment and each subgroup variable will be performed in Cox proportional hazards models with factors for treatment, subgroup variable, and the interaction between treatment and subgroup variable if at least 15 events have occurred in each subgroup category.

The subgroup categories will be examined in Cox proportional hazards models with a factor for treatment group. Kaplan-Meier estimates, HRs, and 95% confidence intervals will be reported if at least 15 events have occurred within the subgroup category. The following subgroup variables and categories will be assessed:

- Age (<65, 65-75, >75 years)
- Sex (Male, Female)
- Race (White, Black, Asian, Other)
- Weight (<70,  $\geq$ 70 kg)
- BMI (<30,  $\geq$ 30 kg/m^2)
- Geographic region (Asia and Australia, Europe, North America, Central and South America)
- Diagnosis of index event (Stroke NIHSS score  $\leq$ 3, Stroke NIHSS score >3, TIA)
- Time from index event to randomisation (<12,  $\geq$ 12 hours)
- Time from index event to loading dose (<12,  $\geq$ 12 hours)
- Diabetes mellitus (Yes, No)
- Hypertension (Yes, No)
- Prior ischaemic stroke or TIA (Yes, No)
- Prior ischaemic heart disease [defined as any of coronary artery bypass grafting, myocardial infarction, percutaneous coronary intervention, or coronary artery disease] (Yes, No)
- Prior ASA (Yes, No)
- Prior statin treatment (Yes, No)
- Smoking status (Current, Former, Never)

The effect of age, weight, BMI, time from index event to randomisation, and time from index event to loading dose may also be further analysed using continuous measurements.

#### **4.2.2 Analysis of the secondary variables**

The secondary variables will be included in the confirmatory testing procedure. Only if the treatment effect on the primary variable is significant at the 4.996% level will the secondary variables be tested in a confirmatory sense in the hierarchical order specified in Section 3.2. The hypothesis testing will continue at the 4.996% significance level until the first statistically non-significant treatment difference ( $p \geq 0.04996$ ) is observed.

The time from randomisation to first subsequent ischaemic stroke will be analysed in the same manner as the primary variable. The proportion of patients with mRS score  $>1$  at Visit 3 will be analysed using a logistic regression model with treatment group, history of stroke, and baseline NIHSS score as explanatory variables. A sensitivity analysis will be performed where missing mRS scores will be imputed as  $>1$ .

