### **1.3 Number of subjects**

At least 647 primary endpoint events are needed to provide 90% power assuming a hazard ratio (HR) of 0.775 in favour of ticagrelor at the significance level of 4.996%, adjusted for the planned efficacy interim analysis (647 events corresponding to a critical value of 0.857). Based on data from the SOCRATES study, a primary endpoint rate of 6.7% in the placebo group is assumed at 30 days following randomisation. Hence, randomising approximately 11000 patients to ticagrelor or placebo in a 1:1 ratio is expected to yield the 647 events needed. The study is event-driven and the final number of randomised patients will be determined based on blind data review.

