#### **3.2 Secondary variables**

The secondary variables, presented in the hierarchical order in which they will be tested, are:

- 1 Time from randomisation to first subsequent ischaemic stroke (including strokes classified as “Undetermined”)
- 2 mRS score >1 at Visit 3

For the time-to-event variable, patients who have not experienced the event will be censored at Visit 3, Day 34, or the date of last event assessment, whichever occurs earlier. If Visit 3 has occurred outside of the visit window (or is missing), see Section 3.1. Furthermore, if the last clinical event assessment has occurred later than the date of death, the date of death will be used as the date of last clinical event assessment (applicable for all time-to-event variables not including death).

The mRS score for patients who have died prior to Visit 3 will by definition be 6. No other imputation for missing data will be made. However, if Visit 3 has occurred prior to Day 30 and the patient has died prior to or at Day 34, the mRS score will be 6.

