#### **4.2.4 Analysis of the exploratory variables**

The time from randomisation to first subsequent stroke or death in patients with ipsilateral atherosclerotic stenosis will be analysed in the same manner as the primary variable.

Analyses in four categories will be performed:

- Patients with ipsilateral atherosclerotic stenosis  $\geq 50\%$  (extracranial and intracranial combined and separately)
- Patients with ipsilateral atherosclerotic stenosis  $\geq 30\%$  (extracranial and intracranial combined and separately) [main category for reporting]
- Patients with atherosclerosis in any vascular bed (including cerebrovascular atherosclerosis or medical history of coronary artery bypass grafting, myocardial infarction, percutaneous coronary intervention, coronary artery disease, or peripheral arterial occlusive disease)

- Patients with ipsilateral stenosis who undergo carotid endarterectomy/intervention

The proportion of patients with subsequent stroke and mRS score  $>2$  at Visit 3 will be analysed using a logistic regression model with treatment group, history of stroke, and baseline NIHSS score as explanatory variables. Additional analyses of disabling stroke will be performed by varying the threshold for the mRS score ( $>1$  and  $>3$ ), and by utilising the 3 categories no stroke, non-disabling stroke (mRS score  $\leq 2$ ), disabling stroke (mRS score  $>2$ ). Strokes need to occur prior to or at the date of the mRS measurement to be classified as non-disabling/disabling.

EQ-5D-5L data will be presented by treatment group using descriptive statistics.

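### Free improvement: the confirmatory model for mRS >1 at Visit 3 omits age and TIA versus stroke, both on file at baseline, and so gives up a modest amount of power

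*SAP*

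**What the plan says.** SAP section 3.2 lists "mRS score >1 at Visit 3" as the second of two secondary variables. Section 4.2.2 makes it confirmatory: "The secondary variables will be included in the confirmatory testing procedure". It is tested at 4.996%, but only after the primary variable and then ischaemic stroke have been significant.

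The same section fixes the model as a "logistic regression model with treatment group, history of stroke, and baseline NIHSS score as explanatory variables" and adds a sensitivity analysis that counts missing mRS scores as >1. Section 4.2.4 uses the same three terms for the exploratory disabling-stroke variable.

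Section 4.2.1.1 shows that two further baseline variables are available:

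- Age is listed as "Age (<65, 65-75, >75 years", and the section allows it to be analysed as a continuous measurement too.
- Index event is listed as "Diagnosis of index event (Stroke NIHSS score", with stroke split at a score of 3 and TIA as a class of its own.

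The SAP gives no reason for stopping at two covariates in the logistic models. It states no rate, effect size or power for mRS >1.

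**The concern.** The plan has already chosen covariate adjustment for mRS >1, so the only question is whether the covariate set uses what is on file. Age and index diagnosis are known at randomisation and can be expected to relate to disability at 30 days. Without index diagnosis in the model, a TIA and a minor stroke with the same NIHSS score get the same expected outcome, although the subgroup section treats them as different index events.

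Randomisation protects the type I error of the planned test. What is at stake is power: in logistic regression, an omitted prognostic covariate moves the treatment log odds ratio towards zero even when the arms are perfectly balanced. This endpoint carries the objective on overall disability.

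**Working it through.** **The plan's own figure.** The only sizing statement concerns the primary endpoint: "At least 647 primary endpoint events are needed to provide 90% power assuming a hazard ratio (HR) of 0.775 in favour of ticagrelor". The level is 4.996% two-sided, so z = 1.960; for 90% power z = 1.282.

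- Events (Schoenfeld) = 4(1.960 + 1.282)² / (ln 0.775)², about 647, or 648 when rounded up. Power with 647 events is 90.0%.
- Critical HR = exp(−2 × 1.960 / √647) = 0.857, as stated.
- Expected events in 11000 patients at 6.7% on placebo: 654 to 656, depending on whether the HR is applied to the risk or to the hazard.

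The design figure reproduces, but it says nothing about mRS >1. Apart from the 11000 patients, 1:1 allocation and the 4.996% level, every input below is an assumption.

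**Measure.** Compare the treatment z under the SAP model with z after adding age and TIA. Gain in effective sample size = (z added / z SAP)² − 1. Power = Φ(|z| − 1.960).

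**Large-sample calculation.** Logistic fits to 400000 records balanced by arm, with standard errors scaled to N = 11000. Assumed: true conditional OR 0.87 (log OR −0.1393), 10% TIA, NIHSS 0 to 5 with log OR 0.4 per point, and log OR 0.5 for stroke history. Covariate strengths are weak (age OR 1.11 per 10 years, TIA OR 0.82), middle (1.35, 0.50) and strong (1.65, 0.22).

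| mRS >1 rate | Strength | z, SAP model | z, with age and TIA | Gain | Power (%) |
|---|---|---|---|---|---|
| 15% | weak | 2.473 | 2.474 | 0.1% | 69.6 to 69.6 |
| 15% | middle | 2.437 | 2.454 | 1.4% | 68.3 to 68.9 |
| 15% | strong | 2.372 | 2.420 | 4.1% | 66.0 to 67.7 |
| 25% | weak | 2.981 | 2.984 | 0.2% | 84.6 to 84.7 |
| 25% | middle | 2.922 | 2.949 | 1.9% | 83.2 to 83.9 |
| 25% | strong | 2.819 | 2.894 | 5.4% | 80.5 to 82.5 |
| 35% | weak | 3.277 | 3.281 | 0.2% | 90.6 to 90.7 |
| 35% | middle | 3.198 | 3.233 | 2.2% | 89.2 to 89.9 |
| 35% | strong | 3.064 | 3.160 | 6.4% | 86.5 to 88.5 |

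Example (25%, middle): (2.949 / 2.922)² − 1 = 0.019.

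**Where the gain comes from.** In that example the log OR moves from −0.1367 to −0.1393, while its standard error rises from 0.0468 to 0.0472. The estimate moves away from zero by more than the standard error grows, so z increases.

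**Second calculation, different inputs.** 400 simulated trials of 11000 patients per scenario. Assumed: intercept −1.95 (mRS >1 in about 22 to 23%), treatment OR 0.88, log OR 0.3 per NIHSS point (0 to 5, with TIA set to 0), log OR 0.4 for stroke history (17% of patients), age SD 11 years, 10% TIA.

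| Age OR per 10 years, TIA OR | Gain | Patients (gain × 11000) | Power (%) |
|---|---|---|---|
| 1.2, 0.6 | 0.45% | about 50 | 77.0 to 77.2 |
| 1.4, 0.5 | 2.2% | about 240 | 78.1 to 79.0 |
| 1.6, 0.4 | 5.3% | about 580 | 76.5 to 78.6 |

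The two calculations agree on the range.

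**Two comparisons.** In the large-sample scenarios, the covariates already in the SAP model are worth about 6 to 12% in effective sample size over no adjustment. For disabling stroke, at an assumed 3% rate and OR 0.80, adding age and TIA gives 0.0%, 0.3% and 1.0% (weak, middle, strong), which is under half a point of power.

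**The case against.** The strongest case against is that this is a preference. The SAP fixes a valid model in advance, it already adjusts for severity and stroke history, and those two covariates secure more than the two proposed would add. All of that stands, and it is why the point is an improvement and not an error. It does not remove the benefit, since the extra covariates are already on file and cost almost nothing.

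Other objections stand in part:

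- **Assumed inputs.** The SAP supplies none of the rates or covariate effects. The upper figures need strong effects, and with weak effects the gain is practically nil.
- **Choice of covariates.** Section 4.2.1.1 lists 16 subgroup variables and does not rank them. Picking age and index diagnosis is a judgement about prognosis. TIA versus stroke is the weaker of the two, because baseline NIHSS captures much of it.
- **Reach.** mRS >1 is tested only after two earlier successes. The power figures above take the test alone at 4.996%.
- **Protocol.** SAP section 6 marks changes from protocol as not applicable, and the protocol is not at hand. If it states the same model, it must be changed too.

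A reader might also infer that precision is being lost, in the sense of a wider confidence interval than necessary. The calculations do not support that: the standard error of the log odds ratio rises slightly on adjustment, and the gain is in power. Nor can a gain be claimed for the disabling-stroke model in section 4.2.4. That variable is exploratory, and at the assumed event rate the gain is 0 to 1%.

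**Conclusion.** The point stands as an optional improvement to one confirmatory model. Section 4.2.2 leaves out two baseline variables that the trial holds. The planned test keeps its type I error but has somewhat less power than the data on file allow. The expected gain from adding both is about 0 to 6% in effective sample size, or 0 to about 2 percentage points of power. This holds for assumed mRS >1 rates of 15 to 35%, a treatment OR of 0.87 to 0.88, 10% TIA, and covariate effects from weak to strong. It is an average: in a single trial, chance imbalance can move the test statistic either way.

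The SAP neither contradicts itself here nor states anything wrong, and nothing suggests that the planned analysis would mislead.

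**What to change.** Before unblinding, amend section 4.2.2 so that the mRS >1 model contains treatment group, history of stroke, baseline NIHSS score, age (continuous, in years) and index diagnosis (TIA versus stroke). Use the same terms in the sensitivity analysis that counts missing scores as >1. If the team prefers the present model, a sentence giving the reason is enough.

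The cost is a short SAP edit and two more model degrees of freedom in about 11000 patients, with no new data. The reported odds ratio becomes conditional on two more covariates, which the report should state. If the protocol gives the same model, amend it to match or declare the departure in SAP section 6. The power argument gives no reason to change section 4.2.4.

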#### **4.2.3 Analysis of the safety variables**

The time-to-event safety variables will be analysed in the same manner as the primary variable, but will not be included in the confirmatory testing procedure. Sensitivity analyses 'on treatment' will be performed (see Section 4.2.1). Subgroup analyses, as specified in Section 4.2.1.1, will be performed for GUSTO Severe bleeding events. Furthermore, the analysis of GUSTO Severe bleeding events will be repeated with event-free patients censored at Visit 4 (or Day 64) instead of Visit 3 (or Day 34).

SAEs, DAEs, and AEs with outcome death summarised by system organ class and preferred term using the Medical Dictionary for Regulatory Activities, will be presented by treatment group using descriptive statistics.

#### **4.2.4 Analysis of the exploratory variables**

The time from randomisation to first subsequent stroke or death in patients with ipsilateral atherosclerotic stenosis will be analysed in the same manner as the primary variable.

Analyses in four categories will be performed:

- Patients with ipsilateral atherosclerotic stenosis  $\geq 50\%$  (extracranial and intracranial combined and separately)
- Patients with ipsilateral atherosclerotic stenosis  $\geq 30\%$  (extracranial and intracranial combined and separately) [main category for reporting]
- Patients with atherosclerosis in any vascular bed (including cerebrovascular atherosclerosis or medical history of coronary artery bypass grafting, myocardial infarction, percutaneous coronary intervention, coronary artery disease, or peripheral arterial occlusive disease)

- Patients with ipsilateral stenosis who undergo carotid endarterectomy/intervention

The proportion of patients with subsequent stroke and mRS score  $>2$  at Visit 3 will be analysed using a logistic regression model with treatment group, history of stroke, and baseline NIHSS score as explanatory variables. Additional analyses of disabling stroke will be performed by varying the threshold for the mRS score ( $>1$  and  $>3$ ), and by utilising the 3 categories no stroke, non-disabling stroke (mRS score  $\leq 2$ ), disabling stroke (mRS score  $>2$ ). Strokes need to occur prior to or at the date of the mRS measurement to be classified as non-disabling/disabling.

EQ-5D-5L data will be presented by treatment group using descriptive statistics.

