### **1.2 Study design**

This is a randomised, placebo-controlled, double-blind, parallel-group, international, multicentre Phase III study to test the hypothesis that ticagrelor and acetylsalicylic acid (ASA) is superior to ASA in preventing stroke and death in patients with acute cerebral ischaemia. Patients with acute ischaemic stroke (AIS) or transient ischaemic attack (TIA) before randomisation and who fulfil all of the eligibility criteria will be randomised within 24 hours of symptom onset in a 1:1 ratio to ticagrelor or placebo, with all patients receiving ASA. The study includes 4 visits: on Day 1 (enrolment/randomisation; Visit 1), on Day 5 to 9 (Visit 2), on Day 30 to 34 (end of treatment period; Visit 3), and on Day 60 to 64 (end of study; Visit 4).

A loading dose of 180 mg ticagrelor or placebo will be given on Day 1 as soon as possible after randomisation. Thereafter, patients will receive either ticagrelor 90 mg twice daily or placebo twice daily. All patients should be treated with open-label ASA.

Approximately 11000 patients will be randomised at approximately 450 study sites. The study is event-driven and the final number of randomised patients will be determined based on blind data review. A data monitoring committee (DMC) will conduct an interim analysis for efficacy after approximately 70% of the primary events have been collected.

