### **3 PRIMARY AND SECONDARY VARIABLES**

#### **3.1 Primary variable**

The primary variable is the time from randomisation to first subsequent stroke or death. Patients who have not experienced either of these events will be censored at Visit 3, Day 34, or the date of last event assessment, whichever occurs earlier. If Visit 3 has occurred within the visit window, Day 30 to 34, events will be included up to the date of Visit 3 (inclusive). If Visit 3 has occurred outside of the visit window (or is missing), it will be replaced by Day 34 for event inclusion and censoring.

Time will be calculated as the number of days plus one between the date of randomisation and the date of the first occurrence of the event, or, if no event has occurred, the date of censoring.

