### **3.4 Exploratory variables**

The exploratory variables are:

- Time from randomisation to first subsequent stroke or death in patients with ipsilateral atherosclerotic stenosis
- mRS score >2 at Visit 3 in patients with subsequent stroke
- EQ-5D-5L profile

For the time-to-event variable, patients who have not experienced the event will be censored at Visit 3, Day 34, or the date of last event assessment, whichever occurs earlier. If Visit 3 has occurred outside the visit window (or is missing), see Section 3.1.

The mRS score for patients who have died prior to Visit 3 will by definition be 6. If Visit 3 has occurred prior to Day 30 and the patient has died prior to or at Day 34, the mRS score will be 6. Furthermore, for the disabling stroke variable (mRS score >2 at Visit 3 in patients with subsequent stroke), the stroke must have occurred prior to or at the date of the mRS measurement.

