## **4 ANALYSIS METHODS**

### **4.1 General principles**

All analyses will be based on the intent-to-treat principle, using the FAS. In time-to-event analyses, the treatment groups will be compared using a Cox proportional hazards model with a factor for treatment group, using the Efron method for ties. P-values and 95% confidence

intervals for the HR will be based on the Wald statistic. In summary tables of these analyses, in addition to HR with confidence intervals and p-values, presentations will include the number and percentage of patients with events and Kaplan-Meier estimates of the event rate per treatment group. Kaplan-Meier estimates of the cumulative proportion of patients with events will be calculated and plotted, with the number of patients at risk indicated below the plot at specific time points. If the total number of events is less than 15, only the number and percentage of patients with events will be presented, but no Kaplan-Meier estimates, HRs, confidence intervals, or p-values.

No multiplicity adjustment will be made to confidence intervals as they will be interpreted descriptively and used as a measure of precision. The primary variable and the secondary variables will be included in a confirmatory testing procedure.

Continuous variables will be summarised by treatment group using descriptive statistics, including the number of patients, mean, standard deviation, median, and range as appropriate. For categorical variables, counts and percentage per treatment group will be presented.

For a description of the critical to quality factors, and processes to ensure the quality of study conduct and the validity of study results, see the Integrated Quality and Risk Management Plan.

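### The carotid-procedure category in SAP 4.2.4 is, as worded, formed after randomisation but analysed from randomisation, so its event rates are distorted and its HR is not a randomised comparison

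*SAP*

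**What the plan says.** SAP 4.2.4 names four categories for the exploratory stenosis analysis. The fourth is "Patients with ipsilateral stenosis who undergo carotid endarterectomy/intervention". No date, window or landmark is attached to the procedure. The third category, just above it, counts past procedures and disease explicitly as history: "medical history of coronary artery bypass grafting, myocardial infarction, percutaneous coronary intervention, coronary artery disease, or peripheral arterial occlusive disease".

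The exploratory variable, in all four categories, "will be analysed in the same manner as the primary variable". For the primary variable, SAP 3.1 states: "The primary variable is the time from randomisation to first subsequent stroke or death". SAP 4.1 specifies a Cox model with treatment group as the only factor, reported with an HR, 95% confidence interval, p-value and Kaplan-Meier estimates. SAP 4.1 also has a sparse-data rule: "If the total number of events is less than 15, only the number and percentage of patients with events will be presented". Under SAP 1.2, patients are "randomised within 24 hours of symptom onset".

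The analysis is exploratory. SAP 4.2.4 makes stenosis of at least 30% the main category for reporting.

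**The concern.** Randomisation falls within a day of symptom onset, and the wording contrasts with the history wording above it. The natural reading is therefore that the procedure comes after randomisation. Follow-up nevertheless starts at randomisation, which creates two problems.

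- **Event rates.** A patient who dies before the procedure cannot enter the category. A patient with a non-fatal stroke before it may be less likely to have the procedure, or more likely. Rates counted from randomisation are then too low or too high.
- **Treatment comparison.** Membership can depend on what happened under treatment, so the arms within the category are not balanced by randomisation. Blinding limits differences in uptake between arms but does not exclude them, because effects on stroke or bleeding can change who has the procedure.

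At stake is an HR with confidence interval, p-value and Kaplan-Meier curve that would read as a randomised subgroup result. The SAP attaches no caveat. Elsewhere it does attend to event order: for disabling stroke, "the stroke must have occurred prior to or at the date of the mRS measurement".

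**Working it through.** The SAP gives no figure for this category, so none can be reproduced. Its design inputs are coherent: for HR 0.775, 90% power and two-sided 4.996%, Schoenfeld's formula gives 648 events, and the stated 647 give 90.0% power.

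**Inputs from the SAP.** From SAP 1.3: "a primary endpoint rate of 6.7% in the placebo group is assumed at 30 days following randomisation", and HR 0.775.

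**Assumptions (not in the SAP).** The procedure is planned uniformly over Day 2 to 16. Uptake is 20% if event-free at the planned time, 20% × m after an earlier non-fatal event, and 0 after death. Deaths are 8% of first events. The hazard is either flat to Day 30 or front-loaded, with half the cumulative hazard in days 0 to 7.

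**Step 1: placebo percentage with events.** The 30-day cumulative hazard is −ln(1 − 0.067) = 0.0694. Let B be the probability of an event before the planned procedure time, and A = 0.067 − B the probability of one after it. Averaging over Day 2 to 16:

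- Flat: the mean cumulative hazard is 0.0694 × 9/30 = 0.0208, so B ≈ 0.0205 and A ≈ 0.0465.
- Front-loaded: the mean is [5 × 0.0347 × 4.5/7 + 9 × 0.0347 × (1 + 4.5/23)]/14 = 0.0346, so B ≈ 0.0340 and A ≈ 0.0330.

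The 20% cancels, and the percentage in the category is (A + 0.92·m·B) / (A + 0.92·m·B + 0.933).

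- Front-loaded, m = 0: 0.0330/0.9660 = 3.4%.
- Front-loaded, m = 4: (0.0330 + 0.1250)/(0.1580 + 0.933) = 14.5%.

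| m | Flat | Front-loaded |
|---|---|---|
| 0 | 4.7% | 3.4% |
| 0.5 | 5.7% | 5.0% |
| 1 | 6.5% | 6.4% |
| 2 | 8.3% | 9.3% |
| 4 | 11.6% | 14.5% |

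The input is 6.7%.

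**Step 2: HR.** The large-sample Cox estimate β solves Σ[d₁ − (d₀ + d₁)·r₁e^β/(r₁e^β + r₀)] = 0. Here d and r are the expected events and numbers at risk in the selected group by arm, on a 0.005-day grid.

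- Constant HR 0.775, equal uptake: 0.774 to 0.781 over all m and both hazards.
- HR 0.70 in week 1 and 0.85 later, front-loaded (0.774 without selection): 0.830 at m = 0 to 0.749 at m = 4.
- The same with the flat hazard: 0.843 to 0.787. Without selection it is about 0.815 (0.70 × 7/30 + 0.85 × 23/30), so the shift is about 0.03 each way.
- Constant 0.775, front-loaded, with event-free ticagrelor uptake 10% lower or 10% higher: 0.775 in both cases at m = 0; 0.816 or 0.741 at m = 1; 0.832 or 0.732 at m = 2.
- A true null with the same uptake differences at m = 2: 1.07 or 0.94.

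**Step 3: a simulation under other assumptions.** Here 15% have an elective procedure uniformly over days 1 to 14, with a constant or strongly front-loaded hazard (Weibull shape 0.4). If an earlier event precludes the procedure, the placebo rate is 5.1% (constant) or 3.0 to 3.1% (front-loaded). If an event leads to the procedure with probability 0.15 or 0.30 (front-loaded), it is 9.0% or 14%. With identical selection in both arms the HR stays near its true value, about 0.78 to 0.80. If benefit exists only before the procedure, the overall HR is 0.88 and the category shows 1.02.

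**Step 4: the 15-event rule.** With constant HR 0.775 and the front-loaded hazard, the pooled event proportion is 3.04% at m = 0 and 13.01% at m = 4. Reaching 15 events takes 15/0.0304 = 494 or 15/0.1301 = about 115 procedure patients. Below that the HR and Kaplan-Meier estimate are suppressed, but the distorted percentage is still printed.

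**The case against.** The strongest reply is that little hangs on this. The category is exploratory, outside the confirmatory procedure and not the main one for reporting. Under a constant effect and equal uptake the HR barely moves, and at m = 1 the placebo percentage is 6.4 to 6.5% against 6.7%. Larger shifts need assumptions that the SAP does not supply, and 6.7% is an all-patient rate, not one for patients with stenosis. Part of the movement in the time-varying case is simply more weight on later events. Sampling error would also dominate: around an HR of 0.775, the approximate 95% interval is 0.28 to 2.13 with 15 events and 0.45 to 1.35 with 50. The protocol may define the timing of the procedure. The disabling-stroke rule classifies an outcome and does not govern entry to a subgroup, so the parallel is loose.

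Most of this stands as a limit on size: the figures are illustrations, and the primary conclusion and type I error are untouched. It does not remove the fault. A wide interval does not turn a selected comparison into a randomised one, and Kaplan-Meier rates from randomisation are misleading here even where the HR is not. If a baseline definition was intended, the SAP wording is wrong and still needs changing.

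**Conclusion.** The concern holds. Followed as written, SAP 4.2.4 conditions on an event after randomisation and counts time from before it. Size and direction cannot be fixed from the SAP.

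Under the stated assumptions the placebo percentage lies between 3.4% and 14.5% instead of 6.7%, and is close to correct only if an earlier stroke hardly changes the chance of the procedure. The HR is nearly preserved with a constant effect and equal uptake. It shifts by roughly 0.03 to 0.06 if uptake differs by 10% between arms (at m = 1 or 2) or if the effect changes over time as assumed (at m = 0 or 4). Whether an HR would be shown at all is unknown, because no procedure rate is given. The point is worth correcting, but it bears on one exploratory category only.

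**What to change.** In SAP 4.2.4, take the fourth category out of the analysis that follows the primary variable. Report by arm, descriptively, the number of patients having the procedure and the numbers of events before and after it. Label this a non-randomised comparison, and give no HR, p-value or Kaplan-Meier estimate from randomisation.

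If an inferential comparison is wanted in this population, make it in a group fixed at randomisation and not defined by the procedure. The extracranial ipsilateral stenosis category of at least 50%, already listed, would serve.

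The change is to SAP wording only. It costs one exploratory HR for a clinically distinct group, and that HR would have had no clear interpretation.
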